#### **2.7.1.1.1 Ancillary Supplies for Participant Use**

The study sites will distribute Sponsor-provided oral thermometers and rulers for use by participants to assess body temperature and injection site reactions, respectively, for recording solicited ARs in the eDiaries. Based on availability, smartphone devices may be provided to those participants who do not have their own device to use for eDiary activities.

#### **2.7.1.2. Safety Telephone Call**

The safety telephone call will be made to the participants by trained study site personnel. This call will follow a Sponsor-approved script, which will facilitate the collection of relevant safety information. Safety telephone calls by the study site to each participant will occur at the time points indicated in the SoA ([Table 1](#) [Part A], [Table 7](#) [Part B], or [Table 11](#) [Part C]). The participant will be interviewed according to the script about the occurrence of AEs, MAAEs, AESIs, SAEs, AEs leading to discontinuation, concomitant medications associated with those events, and any nonstudy vaccinations ([Section 2.7.4.6](#)). All safety information collected from the telephone call must be documented in the source documents as described by the participant and not documented on the script used for the safety telephone call. As noted in [Section 2.7.1.1](#), an unscheduled follow-up safety telephone call may be triggered if an eDiary record results in identification of a relevant safety event.

#### **2.7.1.3. Vital Sign Measurements**

Vital sign measurements include systolic and diastolic blood pressure, heart rate, respiratory rate, and body temperature (preferred route is oral). The participant will be seated for at least 5 minutes before all measurements are taken. Vital signs will be measured at the time points indicated in the SoA ([Table 1](#) [Part A], [Table 7](#) [Part B], or [Table 11](#) [Part C]). On the day of IP administration, vital sign measurements will be collected once before and at least 30 minutes after vaccination. Vital signs may be collected at other study visits in conjunction with a symptom-directed physical examination.

If any of the vital sign measurements meet the toxicity grading criteria for clinical abnormalities of Grade 3 or greater, the abnormal value and grade will be documented in the AE section of the eCRF (unless there is another known cause of the abnormality that would result in an AE classification). The investigator will continue to monitor the participant with additional

assessments until the vital sign value has reached the reference range, returns to the vital sign value at baseline, or is considered stable or until the investigator determines that follow-up is no longer medically necessary.

Participants who are febrile (body temperature  $\geq 38.0\text{ }^{\circ}\text{C}/100.4\text{ }^{\circ}\text{F}$ ) before injection may be rescheduled within the relevant time window period to receive the injection. Afebrile participants with minor illnesses may be vaccinated at the discretion of the investigator.

When procedures overlap and are scheduled to occur at the same timepoint, the order of procedures should be vital sign measurements and then blood collection.

#### **2.7.1.4. Physical Examinations**

A full physical examination, including height and weight, will be performed at the Screening Visit ([Table 1](#) [Part A], [Table 7](#) [Part B], or [Table 11](#) [Part C]). The full physical examination will include an assessment of the skin, head, ears, eyes, nose, throat, neck, thyroid, lungs, heart, cardiovascular system, abdomen, lymph nodes, and musculoskeletal system and extremities. At the Screening Visit, the participant's body mass index will be calculated using the formula weight (kg)/(height [m]). Any clinically significant findings identified should be reported as an MAAE.

Symptom-directed physical examinations may be performed at other time points at the discretion of the investigator. On the day of vaccination, before injection, both arms should be examined, and the associated lymph nodes should be evaluated.

#### **2.7.2. Immunogenicity Assessments**

Blood samples for immunogenicity assessments will be collected at the time points indicated in the SoA ([Table 1](#)). Immunogenicity assessments will be performed for all participants. The following analytes will be measured:

- RSV Abs, as measured by nAbs and binding (bAbs).
- GMT of serum Ab level as measured by a HAI assay for influenza.

Sample aliquots will be designed to ensure that backup samples are available and vial volumes are likely to be adequate for future testing needs. The actual date and time of each sample will be noted. Unique sample identification will be utilized to maintain the blind at the laboratory at all times and allow for automated sample tracking and housing. Handling and preparation of the samples for analysis, as well as shipping and storage requirements, will be provided in a separate study manual.

Measurement of Ab levels will be performed in a laboratory designated by the Sponsor.

According to the ICF ([Section 6.1.6](#)), excess serum from the blood samples collected for immunogenicity testing may be used for future research, which may be performed at the discretion of the Sponsor to further characterize the immune response to RSV and influenza virus and additional assay development.

### **2.7.3. Efficacy Assessments**

While the study will not be powered for efficacy assessments, symptoms of infection with respiratory pathogens will be tracked as an exploratory objective in this study.

### **2.7.4. Safety Definitions and Related Procedures**

#### **2.7.4.1. Adverse Event**

An AE is defined as any untoward medical occurrence associated with the use of an IP in humans, whether or not considered related to the IP.

##### **Events Meeting the Adverse Event Definition:**

- Exacerbation of a chronic or intermittent preexisting condition, including an increase in the frequency and/or intensity of the condition, after administration of the IP.
- New conditions detected or diagnosed after administration of the IP even though they may have been present before the start of the study.

##### **Events NOT Meeting the Adverse Event Definition:**

- Procedures planned before enrollment in the study (eg, hospitalization for preplanned surgical procedure).
- Medical or surgical procedures (eg, endoscopy or appendectomy). The condition that leads to the procedure should be the AE.
- Situations in which an untoward medical occurrence did not occur (social and/or convenience admission to a hospital).

An AR is any AE for which there is a reasonable possibility that the vaccine caused the AE ([Section 2.7.4.3](#)). For the purposes of investigational new drug safety reporting, “reasonable possibility” means that there is evidence to suggest a causal relationship between the IP and AE.

An unsolicited AE is any AE reported by the participant that is not specified as a solicited AR in the protocol ([Section 2.7.4.3](#)) or specified as a solicited AR but starts outside the protocol-defined period for reporting solicited ARs (ie, 7 days after vaccination).

#### **2.7.4.2. Serious Adverse Events**

An AE (including an AR) is considered an SAE if, in the view of either the investigator or Sponsor, it results in any of the following outcomes:

- **Death**  
A death that occurs during the study or that comes to the attention of the investigator during the protocol-defined follow-up period must be reported to the Sponsor, whether or not it is considered related to the IP.
- **Is life-threatening**  
An AE is considered life-threatening if, in the view of either the investigator or the Sponsor, its occurrence places the participant at immediate risk of death. It does not include an AE that, had it occurred in a more severe form, might have caused death.

- **Inpatient hospitalization or prolongation of existing hospitalization**  
In general, inpatient hospitalization indicates the participant was admitted to the hospital or emergency ward for at least one overnight stay for observation and/or treatment that would not have been appropriate in the physician's office or outpatient setting. The hospital or emergency ward admission should be considered an SAE regardless of whether opinions differ as to the necessity of the admission. Complications that occur during inpatient hospitalization will be recorded as AEs; however, if a complication/AE prolongs hospitalization or otherwise fulfills SAE criteria, the complication/AE will be recorded as a separate SAE. Procedures planned before study entry (eg, hospitalization for preplanned surgical procedure) are not considered SAEs.
- **Persistent or significant incapacity or substantial disruption of the ability to conduct normal life functions.** This definition is not intended to include experiences of relatively minor medical significance such as uncomplicated headache, nausea/vomiting, diarrhea, influenza, and accidental trauma (eg, sprained ankle) which may interfere with or prevent everyday life functions but do not constitute a substantial disruption.
- **Congenital anomaly or birth defect.**
- **Medically important event**  
Medical judgment should be exercised in deciding whether SAE reporting is appropriate in other situations, such as important medical events that may not be immediately life-threatening or result in death or hospitalization but may jeopardize the participant or require medical or surgical intervention to prevent one of the other outcomes listed in the above definition. These events should usually be considered serious. Examples of such medical events include allergic bronchospasm requiring intensive treatment in an emergency room or at home, blood dyscrasias or convulsions that do not result in inpatient hospitalization, or the development of drug dependency or drug abuse.

#### 2.7.4.3. **Solicited Adverse Reactions**

The term “reactogenicity” refers to the occurrence and intensity of selected signs and symptoms (ARs) occurring after administration of the IP. The eDiary will solicit daily participant reporting of ARs using a structured checklist ([Section 2.7.1.1](#)). Participants will record such occurrences in an eDiary from the day of injection and 6 subsequent days). Local solicited ARs will be recorded separately for each injection site.

Severity grading of reactogenicity will occur automatically based on participant entry in the eDiary according to the grading scales presented in [Table 4](#) from the toxicity grading scale for healthy adult and adolescent volunteers enrolled in preventive vaccine clinical trials ([DHHS 2007](#)).

If a participant reported a solicited adverse reaction during the solicited period and did not record the event in the eDiary, the event should be recorded on the Reactogenicity page of the eCRF. If the event starts during the solicited period, but continues beyond 7 days after dosing, the participants should notify the site to provide an end date and close out the event on the

Reactogenicity page of the eCRF. If the participant reported an event that started after the solicited period, it should be recorded as an AE on the AE page of the eCRF. All solicited ARs (local and systemic) will be considered causally related to dosing.

**Table 4:      Solicited Adverse Reactions and Grades**

Reaction	Grade 1	Grade 2	Grade 3	Grade 4
Injection site pain	Does not interfere with activity	Repeated use of over-the-counter pain reliever > 24 hours or interferes with activity	Any use of prescription pain reliever or prevents daily activity	Requires emergency room visit or hospitalization
Injection site erythema (redness)	25 – 50 mm/ 2.5 – 5 cm	51 – 100 mm/ 5.1 – 10 cm	> 100 mm/ > 10 cm	Necrosis or exfoliative dermatitis
Injection site swelling/induration (hardness)	25 – 50 mm/ 2.5 – 5 cm	51 – 100 mm/ 5.1 – 10 cm	> 100 mm/ > 10 cm	Necrosis
Axillary (underarm) swelling or tenderness ipsilateral to the side of injection	No interference with activity	Repeated use of over-the-counter (non-narcotic) pain reliever > 24 hours or some interference with activity	Any use of prescription (narcotic) pain reliever or prevents daily activity	Emergency room visit or hospitalization
Headache	No interference with activity	Repeated use of over-the-counter pain reliever > 24 hours or some interference with activity	Significant; any use of prescription pain reliever or prevents daily activity	Requires emergency room visit or hospitalization
Fatigue	No interference with activity	Some interference with activity	Significant; prevents daily activity	Requires emergency room visit or hospitalization
Myalgia (muscle aches all over body)	No interference with activity	Some interference with activity	Significant; prevents daily activity	Requires emergency room visit or hospitalization
Arthralgia (joint aches in several joints)	No interference with activity	Some interference with activity	Significant; prevents daily activity	Requires emergency room visit or hospitalization

Reaction	Grade 1	Grade 2	Grade 3	Grade 4
Nausea/vomiting	No interference with activity or 1-2 episodes/24 hours	Some interference with activity or > 2 episodes/24 hours	Prevents daily activity, requires outpatient intravenous hydration	Requires emergency room visit or hospitalization for hypotensive shock
Chills	No interference with activity	Some interference with activity not requiring medical intervention	Prevents daily activity and requires medical intervention	Requires emergency room visit or hospitalization
Fever (oral)	38.0 – 38.4°C 100.4 – 101.1°F	38.5 – 38.9°C 101.2 – 102.0°F	39.0 – 40.0°C 102.1 – 104.0°F	> 40.0°C > 104.0°F

Abbreviations: AE = adverse event; eCRF = electronic case report form.

Note: Events listed in the table above but starting >7 days after study injection will be recorded on the AE page of the eCRF. Causality for each event will be determined per assessment by the investigator.

Source: Guidance for Industry – Toxicity Grading Scale for Healthy Adult and Adolescent Volunteers Enrolled in Preventive Vaccine Clinical Trials ([DHHS 2007](#)).

Any solicited AR that meets any of the following criteria must be entered into the participant's source document and must also be recorded by the study site staff on the solicited AR page of the participant's eCRF:

- Solicited local or systemic AR that results in a visit to a healthcare practitioner (HCP), to be recorded as an MAAE ([Section 2.7.4.4](#)).
- Solicited local or systemic AR leading to the participant withdrawing from the study or the participant being withdrawn from the study by the investigator (AE leading to withdrawal).
- Solicited local or systemic AR lasting beyond 7 days post-injection.
- Solicited local or systemic AR that otherwise meets the definition of an SAE.

#### 2.7.4.4. Medically Attended Adverse Events

An MAAE is an AE that leads to an unscheduled visit to an HCP, including telephone calls. This would include visits to a study site for unscheduled assessments (eg, rash assessment) and visits to HCPs external to the study site (eg, urgent care, primary care physician). The investigators will review unsolicited AEs for the occurrence of any MAAEs. Unsolicited AEs will be captured on the AE page of the eCRF.

#### 2.7.4.5. Adverse Event of Special Interest

An AESI is an AE (serious or nonserious) of scientific and medical concern specific to the Sponsor's product or program for which ongoing monitoring and immediate notification by the investigator to the Sponsor is required and documentation is in the form of a case narrative. Such events may require further investigation to characterize and understand them.

[Section 6.3](#) provides a list of the AESIs pertinent to this study.

All AESIs will be collected from Day 1 through EoS and must be reported to the Sponsor (or designee) immediately and in all circumstances within 24 hours of becoming aware of the event via the electronic data capture (EDC) system. If a site receives a report of a new AESI from a study participant or receives updated data on a previously reported AESI at a time after the eCRF has been taken offline, then the site can report this information on a paper AESI form using the SAE Mailbox or the SAE Fax line ([Section 2.7.4.10](#)).

#### **2.7.4.5.1 Anaphylaxis**

All suspected cases of anaphylaxis should be recorded as MAAEs and reported as an SAE, based on the criteria for a medically important event, unless the event meets other serious criteria. As an SAE, the event should be reported to the Sponsor (or designee) immediately and in all circumstances within 24 hours per [Section 2.7.4.10](#). The investigator will submit any updated anaphylaxis case data to the Sponsor within 24 hours of it being available. For reporting purposes, a participant who displays signs or symptoms consistent with anaphylaxis should be reported as a potential case of anaphylaxis. This is provided as general guidance for investigators and based on the Brighton Collaboration case definition ([Rüggeberg, et al 2007](#)).

Anaphylaxis is an acute hypersensitivity reaction with multiorgan system involvement that can present as, or rapidly progress to, a severe life-threatening reaction. It may occur following exposure to allergens from a variety of sources.

Anaphylaxis is a clinical syndrome characterized by the following:

- Sudden onset AND
- Rapid progression of signs and symptoms AND
- Involves 2 or more organ systems, as follows:
  - **Skin/mucosal:** Urticaria (hives), generalized erythema, angioedema, generalized pruritus with skin rash, generalized prickle sensation, and red and itchy eyes.
  - **Cardiovascular:** Measured hypotension, clinical diagnosis of uncompensated shock, loss of consciousness or decreased level of consciousness, and evidence of reduced peripheral circulation.
  - **Respiratory:** Bilateral wheeze (bronchospasm), difficulty breathing, stridor, upper airway swelling (lip, tongue, throat, uvula, or larynx), respiratory distress, persistent dry cough, hoarse voice, sensation of throat closure, sneezing, and rhinorrhea.
  - **Gastrointestinal:** Diarrhea, abdominal pain, nausea, and vomiting.

#### **2.7.4.5.2 Myocarditis/Pericarditis**

A case of suspected, probable, or confirmed myocarditis, pericarditis, or myopericarditis should be reported as an AESI, even if it does not meet the criteria per the CDC case definition. The event should also be reported as an SAE if it meets seriousness criteria ([Section 2.7.4.2](#)). The CDC case definition is provided in [Section 6.3.2](#) as guidance.

#### **2.7.4.6. Eliciting and Documenting Adverse Events**

The investigator is responsible for ensuring that all AEs and SAEs are recorded in the eCRF and reported to the Sponsor.

Solicited ARs will be collected from the day of injection and 6 subsequent days. Other (unsolicited) AEs will be collected from the day of injection and 28 subsequent days.

The MAAEs, AESIs, AE leading to withdrawal, and SAEs will be collected from participants as specified in the SoA ([Table 1 \[Part A\]](#) [Table 7 \[Part B\]](#), or [Table 11 \[Part C\]](#)) until the end of their participation in the study. Any AEs occurring before administration of the IP will be analyzed separately from the AEs occurring after administration of the IP.

At every study site visit or safety telephone call, participants will be asked a standard question to elicit any medically related changes in their well-being according to the scripts provided. Participants will also be asked if they have been hospitalized, had any accidents, used any new medications, changed concomitant medication regimens (both prescription and over-the-counter medications), or had any nonstudy vaccinations.

In addition to participant observations, physical examination findings or data relevant to participant safety classified as an AE will be documented on the AE page of the eCRF.

After the initial AE/SAE report, the investigator is required to proactively follow each participant at subsequent study site visits, safety telephone calls, and any other contact. All AEs and SAEs will be treated as medically appropriate and followed until resolution, stabilization, the event is otherwise explained, or the participant is LTFU ([Section 2.6.3](#)). All contacts or contact attempts concerning the follow-up of AEs and SAEs should be recorded in the participant's source documentation.

Pregnancies occurring in participants after enrollment must be reported to Sponsor or designee within 24 hours of the site learning of its occurrence. If the participant agrees to submit this information, the pregnancy must be followed to determine the outcome, including spontaneous or voluntary termination, details of the birth, and the presence or absence of any birth defects, congenital abnormalities, or maternal and/or newborn complications. This follow-up should occur even if the intended duration of the safety follow-up for the study has ended. Pregnancy report forms will be distributed to the study site to be used for this purpose. The investigator must immediately (within 24 hours of awareness) report to the Sponsor any pregnancy resulting in an abnormal outcome according to the procedures described for SAEs ([Section 2.7.4.10](#)).

#### **2.7.4.7. Assessment of Intensity**

An event is defined as “serious” when it meets at least one of the predefined criteria as described in the definition of an SAE ([Section 2.7.4.2](#)), NOT when it is rated as severe.

The severity (or intensity) of an AR or AE refers to the extent to which it affects the participant's daily activities. The toxicity grading scale for healthy adult and adolescent volunteers enrolled in preventive vaccine clinical trials ([DHHS 2007](#)) will be used to categorize local and systemic reactogenicity events (solicited ARs), clinical laboratory test results, and vital sign measurements observed during this study. Specific criteria for local and systemic reactogenicity events are presented in [Section 2.7.4.3](#).

The determination of the severity for all unsolicited AEs should be made by the investigator based upon their medical judgment and the definitions of severity as follows:

- **Mild:** These events do not interfere with the participant's daily activities.
- **Moderate:** These events cause some interference with the participant's daily activities and require limited or no medical intervention.
- **Severe:** These events prevent the participant's daily activity and require intensive therapeutic intervention.

The study staff should elicit from the participant the impact of AEs on the participant's activities of daily living to assess the severity and document the AE appropriately in the participant's source documentation. Changes in the severity of an AE should be documented in the participant's source documentation to allow an assessment of the duration of the event at each level of intensity to be performed. An AE characterized as intermittent requires documentation of the date of onset and duration of each episode. An AE that fluctuates in severity during the course of the event is reported once in the eCRF at the highest severity observed.

#### **2.7.4.8. Assessment of Causality**

The investigator's assessment of an AE's relationship to IP is part of the documentation process but is not a factor in determining what is or is not reported in the study.

The investigator will assess the causality (ie, whether there is a reasonable possibility that the IP caused the event) for all AEs and SAEs. The relationship will be characterized using the following classification:

- **Not related:** There is not a reasonable possibility of a relationship to the IP. The participant did not receive the IP, OR temporal sequence of the AE onset relative to administration of the IP is not reasonable, OR the AE is more likely explained by another cause than the IP.
- **Related:** There is a reasonable possibility of a relationship to the IP. There is evidence of exposure to the IP. The temporal sequence of the AE onset relative to the administration of the IP is reasonable. The AE is more likely explained by the IP than by another cause.

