#### **2.7.4.10. Reporting Serious Adverse Events**

Prompt notification by the investigator to the Sponsor of an SAE is essential so that legal obligations and ethical responsibilities toward the safety of participants and the safety of a study intervention under clinical investigation are met.

Any AE considered serious by the investigator or that meets SAE criteria ([Section 2.7.4.2](#)) must be reported to the Sponsor immediately (within 24 hours of becoming aware of the SAE) via the EDC system. The investigator will assess whether there is a reasonable possibility that the IP caused the SAE. The Sponsor will be responsible for notifying the relevant regulatory authorities of any SAE as outlined in 21 CFR Parts 312 and 320. The investigator is responsible for notifying the IRB directly.

If the eCRF is unavailable at the time of the SAE, the following contact information is to be used for SAE reporting:

- SAE Mailbox: [[contact]](mailto:[contact])
- SAE Fax Line (USA and Canada): [contact]

Regulatory reporting requirements for SAEs are described in [Section 2.7.4.15](#).

The investigator and any qualified designees are responsible for detecting, documenting, and recording events that meet the definition of an AE, including SAEs, and remain responsible for following up AEs that are serious, considered related to the IP or study procedures, or that caused the participant to discontinue the study.

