#### **2.5.3.2.2. TEAEs by System Organ Class and Preferred Term**

The following summary tables of unsolicited TEAEs up to 28 days after injection will be provided by SOC and PT using frequency counts and percentages (i.e., number and percentage of participants with an event):

- All unsolicited TEAEs
- All unsolicited TEAEs that are treatment-related
- All serious TEAEs
- All serious TEAEs that are treatment-related
- All unsolicited non-serious TEAEs
- All unsolicited non-serious severe TEAEs
- All unsolicited medically-attended TEAEs
- All unsolicited medically-attended TEAEs that are treatment-related
- All unsolicited TEAEs leading to study discontinuation
- All unsolicited severe TEAEs
- All unsolicited severe TEAEs that are treatment-related
- All unsolicited treatment emergent AESI

Note: Severe TEAEs include both unsolicited severe TEAEs and  $\geq$  Grade 3 solicited ARs that meet SAE criteria after injection.

Summary tables will also be provided for number and percentage of participants with unsolicited TEAEs up to 7 days post-injection, between 8 to 28 days post-injection, and up to 28 days post-injection, and be presented by SOC and PT.

Additionally, summary tables of SAEs, treatment-related SAEs, MAAEs, treatment-related MAAEs, TEAEs leading to study discontinuation, AESIs, and TEAEs leading to death will be also provided by SOC and PT considering all events reported throughout the study. Number of events and number of participants will also be summarized by SOC and PT for participants with AESI up to 7 days post-injection, up to 28 days post-injection, and throughout the study.

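### Protocol 2.7.4.8 mixes two causality standards, so an event with a likelier alternative cause can be classed either way and the treatment-related tables may be too low

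*Protocol*

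**What the plan says.** Protocol 2.7.4.8 has the investigator assess, for every AE and SAE, "whether there is a reasonable possibility that the IP caused the event". Two classes are offered.

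- **Related** opens with "There is a reasonable possibility of a relationship to the IP". It goes on to exposure and plausible timing, and ends with "The AE is more likely explained by the IP than by another cause".
- **Not related** opens with the absence of a reasonable possibility. It then lists three conditions joined by OR: no IP received, implausible timing, and finally "OR the AE is more likely explained by another cause than the IP".

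Sections 3.7.4.8 and 4.7.4.8 carry this rule into Parts B and C by cross-reference.

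Elsewhere only reasonable possibility appears. Protocol 2.7.4.1 defines an adverse reaction by it and explains, for IND safety reporting, that the term "means that there is evidence to suggest a causal relationship between the IP and AE". Protocol 2.7.4.10 says of SAEs: "The investigator will assess whether there is a reasonable possibility that the IP caused the SAE". SAP 2.5.3.1 defines an AR by the same standard.

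Relationship to IP is recorded for unsolicited AEs (Protocol 2.7.4.9). The SAP tabulates treatment-related events in 2.5.3.2.1, 2.5.3.2.2 and 2.5.3.2.4, for example "All serious TEAEs that are treatment-related", and gives no definition of treatment-related of its own.

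**The concern.** The two standards are not equivalent. Reasonable possibility asks whether there is evidence pointing to the vaccine. The comparison asks which cause is likelier. An event can pass the first and fail the second, and 2.7.4.8 does not say which prevails.

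Events with competing causes are foreseeable here. Participants are 50 or older and may have chronic diagnoses (inclusion criterion 1 of Parts A and B). In Part B, AESIs must be reported even when they arise during or after COVID infection (Protocol 6.3.2). Myocarditis after an mRNA vaccine in someone with recent COVID-19 is an example. One investigator could class it as related on reasonable possibility; another who thinks infection likelier could class it as not related. Both could cite 2.7.4.8.

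At stake are the treatment-related tables and the few steps that turn on relatedness: continuing responsibility for following up related AEs (2.7.4.10), and notification of SAEs learned of after a participant has left the study (2.7.4.12).

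**Working it through.** No sample size, power or rate is involved, so there is no figure in the plan to reproduce. The check compares the texts and then tries the two classes on every kind of event.

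**Standards side by side**

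| Place | Standard |
|---|---|
| Protocol 2.7.4.1, AR definition | Reasonable possibility |
| SAP 2.5.3.1, AR definition | Reasonable possibility |
| Protocol 2.7.4.10, SAE question | Reasonable possibility |
| Protocol 2.7.4.8, question and opening of each class | Reasonable possibility |
| Protocol 2.7.4.8, end of Related | IP likelier than another cause |
| Protocol 2.7.4.8, last OR condition of Not related | Another cause likelier than the IP |

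**Case check**

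| Event | By reasonable possibility | By the comparative clauses |
|---|---|---|
| (a) IP likelier than another cause | Related | Related |
| (b) IP and another cause equally likely, each a reasonable possibility | Related | Neither clause met |
| (c) Another cause likelier, reasonable possibility of the IP remains | Related | Not related |
| (d) No reasonable possibility of the IP | Not related | Not related |

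The standards agree on (a) and (d) and part on (b) and (c). In (c) the conflict lies inside 2.7.4.8 itself: the opening of Related is true, and so is a condition sufficient for Not related.

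**Direction.** Suppose the comparison governs, so that an event must have a reasonable possibility and also have the IP as the likelier cause. Related events are then a subset of those with a reasonable possibility. Events can leave the Related class through this clause; none can enter.

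**Size.** The documents give no number of events in (b) or (c). As an assumption, take 10 events with two plausible causes. All 10 are related on reasonable possibility. On the comparative reading, those in which the vaccine is judged likelier stay, which could be any number from 0 to 10. The shortfall then lies between 10 − 10 = 0 and 10 − 0 = 10. That range shows only that the size is undetermined.

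**Reach.**
- *Can move:* treatment-related unsolicited TEAEs (overall, by SOC and PT, by severity), SAEs, MAAEs and severe TEAEs, and steps triggered by relatedness.
- *Cannot move:* total AE and SAE counts, because 2.7.4.8 says causality does not decide what is reported; solicited ARs, all treated as related (Protocol 2.7.4.3, SAP 2.5.3.1); and the primary safety endpoints, none of which uses relatedness (SAP 2.2.1.1, 3.2.1.1, 4.2.1.1).

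**The case against.** The strongest reply is that 2.7.4.8 never abandons reasonable possibility. The question is put in those terms and each class opens with them, so a sensible investigator will read the comparison as guidance. Section 2.7.4.10 repeats the question without the comparison and offers no rival classes. All AEs are reported whatever their cause. One rule applies to all arms of Parts A and B under an observer blind. Only descriptive tables and a few procedural steps could change.

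Much of this stands, and it rules out several stronger readings that a reader might infer:

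- *An event is related only if the vaccine beats every other cause.* The text says another cause, not any other. It does not state that the four sentences under Related must all hold, although the contrast with the OR list under Not related makes that reading natural.
- *Ties have no class.* A tie meets neither comparative clause, but the opening sentence can place it as related.
- *Treatment-related events are undercounted.* No document shows this; it depends on which wording investigators follow.
- *Expedited safety reports will fall.* Section 2.7.4.15 ties those reports to regulatory requirements and Sponsor policy, not to the 2.7.4.8 class. The explanation of reasonable possibility in 2.7.4.1 is given expressly for IND safety reporting.
- *Sites will split according to whether they follow 2.7.4.8 or 2.7.4.10.* Only 2.7.4.8 supplies classes, so the conflict is within that section.

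What does not stand is that the wording is harmless. The last Not related condition is joined by OR and so is sufficient on its face; for case (c) it contradicts the opening of Related and the AR definitions. Complete reporting protects total counts, not the related subset. A common rule across arms limits distortion between arms but not in the level, and Part C has no concurrent comparator.

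**Conclusion.** The point holds as an internal contradiction in a stated rule. Section 2.7.4.8 combines reasonable possibility with a likelier-cause test, and the second conflicts with Protocol 2.7.4.1 and 2.7.4.10 and SAP 2.5.3.1. Treatment-related counts in all three parts may be too low if investigators let the comparison govern.

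The direction follows from the subset argument and assumes that the comparative sentence is treated as necessary for Related. The size cannot be derived from the documents and could be nil. Because the SAP takes treatment-related as collected, it cannot resolve the ambiguity at the analysis stage. The point is worth correcting, but it does not threaten the primary safety analysis.

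**What to change.** Delete both comparative clauses from Protocol 2.7.4.8. Related then means a reasonable possibility, with exposure and plausible timing, even where another cause is also possible; Not related means no reasonable possibility. Sections 2.7.4.1, 2.7.4.8 and 2.7.4.10 and SAP 2.5.3.1 then share one standard, and ties fall under Related. Sections 3.7.4.8 and 4.7.4.8 follow by cross-reference. Send a clarification to sites for any part still collecting data.

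The change cannot reach data already collected unless events are reassessed. SAP 2.3.4 records that the Part A EDC database had been locked by the time the IRT error was reported on 07 March 2023. For such data, state in the SAP or CSR which causality wording lies behind the treatment-related tables.

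The text change is two clauses and a site notice. The costs are that somewhat more events will be labelled related, and that the parts may differ in the wording applied. The second matters because SAP 4.5.3.2 allows Part B AE data to be summarised on the Part C Safety Set; any such table of related events should carry a note on the wording used.
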